2.0 Goals

2.1 Primary Goal

To determine the efficacy of the combination of binimetinib and encorafenib as $\geq 2nd$ line of treatment for patients with metastatic pancreatic cancer with BRAF^{V600E} mutation.

- 2.11 Primary Endpoint Objective response rate at 24 weeks post-registration, as defined by RECIST 1.1.
- 2.2 Secondary Goals To determine in patients treated with the combination of binimetinib and encorafenib as ≥ 2nd line of treatment for patients with metastatic pancreatic cancer with BRAF^{V600E} mutation:
 - 2.21 The median progression-free survival Endpoint: The median time from study registration to clinical or radiographic disease progression or death, whichever occurs first, as defined by RECIST 1.1.
 - 2.22 The median overall survival Endpoint: The median time from study registration to death.
 - 2.23 Duration of Response Endpoint: The median duration of time from first documentation of an objective response to the earliest date progression is documented.
 - 2.24 Time to Response Endpoint: The median duration of time from study registration to the first documentation of an objective response.
 - 2.25 The safety and tolerability Endpoint: The rate of grade 3+ Adverse Events as defined by NIH CTCAE v5.0.
- 2.3 Correlative Research Goal
 - 2.31 To determine the mechanisms of resistance, either primary or acquired through real time monitoring of the BRAF mutational profile evolution.
 - 2.32 Endpoint: Additional mutations in BRAF or in other related genes as determined by nextgeneration sequencing from plasma samples.

3.0 Patient Eligibility NOTE: Waivers to eligibility criteria are not allowed per ACCRU policy

- 3.1 Pre-registration Inclusion Criteria
 - 3.11 Age ≥ 18 years.
 - 3.12 Histological confirmation of a pancreatic malignancy as confirmed by the local pathology lab

- 3.13 Patients whose disease has progressed on (or who were intolerant of) at least one line of therapy for metastatic disease
- 3.14 Patients whose disease has recurred with metastatic disease ≤12 weeks of completion of neoadjuvant or adjuvant systemic chemotherapy; or patients with locally advanced disease whose disease progressed to metastatic disease on, or ≤12 weeks after completion of systemic chemotherapy would also be eligible
- 3.15 Provide informed written consent ≤ 28 days prior to pre-registration.

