 - 3.34 Any of the following because this study involves an investigational agent whose genotoxic, mutagenic and teratogenic effects on the developing fetus and newborn are unknown:
 - Pregnant women
 - Nursing women
 - Men or women of childbearing potential who are unwilling to employ adequate contraception

NOTE: Female participants of childbearing potential must agree to use methods of contraception that are highly effective or acceptable, as described in Appendix II, and to not donate ova from Screening until 30 days after the last dose of study drug.

NOTE: Male participants must agree to use methods of contraception that are highly effective or acceptable, as described in Appendix II, and to not donate sperm from Screening until 90 days after the last dose of study drug.

- 3.35 Co-morbid systemic illnesses or other severe concurrent disease which, in the judgment of the investigator, would make the patient inappropriate for entry into this study or interfere significantly with the proper assessment of safety and toxicity of the prescribed regimens.
- 3.36 Immunocompromised patients and patients known to be HIV positive and currently receiving antiretroviral therapy. NOTE: Patients known to be HIV positive, but without clinical evidence of an immunocompromised state, are eligible for this trial.
- 3.37 Uncontrolled intercurrent illness including, but not limited to, ongoing or active infection, symptomatic congestive heart failure, cardiac arrhythmia, or psychiatric illness/social situations that would limit compliance with study requirements.
- 3.38 History of acute coronary syndromes (including myocardial infarction, unstable angina, coronary artery bypass grafting, coronary angioplasty or stenting) < 6 months prior to registration.
- 3.39a Left ventricular ejection fraction (LVEF) ≤50% as determined by MUGA or ECHO.
- 3.39b Uncontrolled hypertension defined as persistent systolic blood pressure \geq 150/100 mmHg or diastolic blood pressure \geq 100 mmHg despite current therapy.
- 3.39c Triplicate average baseline QTc interval \geq 480 ms.
- 3.39d Receiving any other investigational agent which would be considered as a treatment for the primary neoplasm.

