- 3.39e Patients who have had another active malignancy within the past two years are ineligible EXCEPT FOR patients with cervical cancer in situ, in situ carcinoma of the bladder, non-melanoma carcinoma of the skin, or patients who have had therapy with curative intent for breast or prostate cancer, but remain on adjuvant hormonal therapy.
- 3.39f Received anticancer therapy including chemotherapy, immunotherapy, or antineoplastic biologic therapy (e.g., erlotinib, cetuximab, bevacizumab etc.), ≤ 14 days (≤ 28 days for an antibody-based therapy) prior to registration.
- 3.39g Patients who have undergone major surgery (e.g., in-patient procedures) ≤ 6 weeks prior to registration or who have not recovered from side effects of such procedure.
- 3.39h Patients who have had radiotherapy ≤14 days prior to registration or who have not recovered from side effects of such procedure. NOTE: Palliative radiation therapy must be complete 7 days prior to the first dose of study treatment.
- 3.39i Patient has not recovered to \leq Grade 1 from toxic effects of prior therapy before registration.

EXCEPTIONS: Stable chronic conditions (\leq Grade 2) that are not expected to resolve (such as neuropathy, myalgia, alopecia, prior therapy-related endocrinopathies).

3.39j Uncontrolled or symptomatic brain metastases or leptomeningeal carcinomatosis that are not stable, require steroids, are potentially life-threatening or have required radiation ≤28 days prior to registration.

NOTE: Patients with previously treated brain metastases may participate provided they are stable (e.g., without evidence of progression by radiographic imaging for ≤ 28 days prior to registration and neurologic symptoms have returned to baseline), and have no evidence of new or enlarging brain metastases or CNS edema, and does not require steroids at least 7 days before the first dose of study treatment.

- 3.39k Impairment of gastrointestinal function or disease which may significantly alter the absorption of study drug (e.g., active ulcerative disease, uncontrolled vomiting or diarrhea, malabsorption syndrome, small bowel resection with decreased intestinal absorption), or recent (≤12 weeks) history of a partial or complete bowel obstruction, or other condition that will interfere significantly with the absorption or oral drugs.
- 3.391 Known history of acute or chronic pancreatitis.

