- 3.39m Concurrent neuromuscular disorder that is associated with elevated CK (e.g., inflammatory myopathies, muscular dystrophy, amytrophic lateral sclerosis, spinal muscular atrophy).
- 3.39n History or current evidence of RVO or current risk factors for RVO (e.g., uncontrolled glaucoma or ocular hypertension, history of hyperviscosity or hypercoagulability syndromes); history of retinal degenerative disease.
- 3.390 Current use of prohibited medication (including herbal medications, supplements, or foods), as described in Section 9.6, or use of prohibited medication \leq 7 days prior to registration.
- 3.39p History of thromboembolic or cerebrovascular events ≤ 12 weeks prior to registration. Examples include transient ischemic attacks, cerebrovascular accidents, hemodynamically significant (i.e. massive or sub-massive) deep vein thrombosis or pulmonary emboli.

NOTE: Patients with either deep vein thrombosis or pulmonary emobli that do not result in hemodynamic instability are allowed to enroll as long as they are on a stable dose of anticoagulants for ≤ 4 weeks prior to registration.

NOTE: Patients with thromboembolic events related to indwelling catheters or other procedures may register.

3.39q Evidence of Hepatitis B Virus (HBV) or Hepatitis C Virus (HCV) infection.

NOTE: Patients with laboratory evidence of cleared HBV or HCV infection may

register.

NOTE: Patients with no prior history of HBV infection who have been vaccinated against HBV and who have a positive antibody against hepatitis B surface antigen as the only evidence of prior exposure may register.

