8.0 Dosage Modification Based on Adverse Events

Strictly follow the modifications in this table for the first **two** cycles, until individual treatment tolerance can be ascertained. Thereafter, these modifications should be regarded as guidelines to produce mild-to-moderate, but not debilitating, side effects. If multiple adverse events are seen, administer dose based on greatest reduction required for any single adverse event observed. Reductions or increases apply to treatment given in the preceding cycle and are based on adverse events observed since the prior dose.

ALERT: ADR reporting may be required for some adverse events (See Section 10)

8.1 Dose Levels (Based on Adverse Events in Tables 8.2 and 8.3), if applicable – This is potentially different information than what is found in the tables in Section 7.0.

Dose		
Level	Encorafenib	Binimetinib
0	450 mg	45 mg
-1	300 mg	30 mg
-2	225 mg	15 mg

* Dose level 0 refers to the starting dose.

The lowest recommended dose level of encorafenib is 225 mg QD and the lowest recommended dose level of binimetinib is 15 mg BID. When the AE that resulted in a dose reduction improves to and remains stable at the patient's baseline level for a minimum of 14 days, the dose can be re-escalated to the next dose level at the discretion of the Investigator, provided there are no other concomitant toxicities that would prevent drug re-escalation. There is no limit to the number of times the patient can have their dose reduced or re-escalated, however:

- No dose re-escalation of encorafenib is allowed after a dose reduction due to prolonged QTcF ≥ 501 msec
- No dose re-escalation of binimetinib is allowed after a dose reduction due to LVEF dysfunction
- No dose re-escalation of binimetinib or encorafenib is allowed after a dose reduction due to retinal toxicity ≥ Grade 2.
- If binimetinib is withheld, consider reducing encorafenib to a maximum dose of 300 mg daily until binimetinib is resumed.

Please refer to Dose Modification Table for recommended dose modifications for encorafenib and/or binimetinib, if applicable, based on the occurrence of treatment-related AEs.

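### Two eligibility stability notes, 3.39p (anticoagulation) and 3.39j (brain metastases), print a maximum period where a minimum is needed

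*Combined protocol and SAP*

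**What the plan says.** Section 3.39p excludes patients with "History of thromboembolic or cerebrovascular events ≤ 12 weeks prior to registration". Its examples include transient ischaemic attacks, strokes and "hemodynamically significant (i.e. massive or sub-massive) deep vein thrombosis or pulmonary emboli". Two notes follow. The first admits DVT or PE without haemodynamic instability, "as long as they are on a stable dose of anticoagulants for ≤ 4 weeks prior to registration". The second reads "Patients with thromboembolic events related to indwelling catheters or other procedures may register" and attaches no anticoagulant condition.

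Section 3.39j has a note of the same form. Previously treated brain metastases are acceptable if stable. The example given of stability is no radiographic progression for a period printed as ≤ 28 days before registration. The same sentence sets the steroid-free period as a minimum of 7 days before the first dose.

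No other section states a minimum period of anticoagulation or of radiographic stability.

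**The concern.** Both notes are meant to let in patients whose condition has settled. A condition of that kind needs a lower bound on how long the settled state has lasted. With an upper bound, the notes favour the patients whose state is least established.

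Section 15.17 lists PE, DVT and gastrointestinal haemorrhage as uncommon binimetinib toxicities (0.1% to under 1%), and 15.184 warns of serious or fatal bleeding. A clot only days into anticoagulation is plausibly what the 3.39p note was meant to hold back, although the protocol does not say so.

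Eligibility also has a statistical role. Under 13.6, a patient found not to have met every criterion at registration is ineligible and moves to event monitoring. Under 16.21, only eligible patients are evaluable for the primary endpoint. Sites and auditors therefore need a single reading of each note.

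**Working it through.** The plan gives no figure to reproduce here, so the check is on the direction of the inequality and on the surrounding text.

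**Inputs.** The period in 3.39p is 4 weeks = 4 × 7 = 28 days. The parent look-back is 12 weeks = 12 × 7 = 84 days. The period in 3.39j is 28 days.

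**Step 1: who meets each note.** Let d be the number of days on a stable anticoagulant dose (3.39p), or without radiographic progression (3.39j), at registration. For 3.39p, this concerns haemodynamically stable clots within 84 days that are not related to a catheter or procedure.

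| d | As printed (d ≤ 28) | As a minimum (d ≥ 28) |
|---|---|---|
| 2 days | meets | does not meet |
| 0 to 27 days | meets | does not meet |
| exactly 28 days | meets | meets |
| 35 days (5 weeks) | does not meet | meets |
| over 28 days | does not meet | meets |

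The two versions agree only at exactly 28 days. These are durations, not patient counts.

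**Step 2: could the sign be a look-back?** The protocol often uses ≤ before a number of days to mean within that many days of registration, as in 3.39h: "Patients who have had radiotherapy ≤14 days prior to registration". There it dates an event. In 3.39p and 3.39j the word *for* precedes the sign, so the phrase measures how long a state has lasted. Two stability notes with the same construction suggest a drafting habit meaning throughout the last N days. A patient stable throughout the last 28 days has been stable for at least 28 days, so that intent is the same as d ≥ 28.

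**Step 3: how the protocol writes a minimum elsewhere.** Section 8.1 allows dose re-escalation once the adverse event has stayed at the patient's "baseline level for a minimum of 14 days". The steroid condition in 3.39j is also worded as a minimum. The two printed signs therefore differ from the protocol's own plain usage.

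**Step 4: what follows from failing a note.** For 3.39p there are two readings of the parent criterion.
- Broad: it names thromboembolic events in general, so a stable clot within 84 days is excluded unless a note admits it. A patient stable for 35 days is then excluded.
- Narrow: its DVT/PE examples are only haemodynamically significant ones, so a stable clot was never excluded. Failing the note then has no effect, but the note's condition would have no function.

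For 3.39j the consequence is softer still. The 28-day period is given only as an example of stability, and the parent criterion concerns uncontrolled or symptomatic disease.

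**The case against.** The best defence is that investigators will read both notes as intended. The repeated construction supports a house idiom, and on that reading the rule is already right. This stands as an account of probable intent. It does not make the text clear, and the proposed wording states that same intent.

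Other safeguards exist. Section 3.35 excludes co-morbidity which, "in the judgment of the investigator, would make the patient inappropriate for entry into this study". Section 3.37 excludes uncontrolled intercurrent illness, which could cover a very recent clot. Section 3.39n treats hypercoagulability syndromes as a risk factor for retinal vein occlusion. These can keep out a recently anticoagulated patient, but none sets a minimum period.

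A reader might infer that a patient stable for 5 weeks is definitely barred and cannot be readmitted, because Section 3.0 says "Waivers to eligibility criteria are not allowed per ACCRU policy". The documents do not support that as a firm conclusion. The bar on waivers matters only under the broad reading of the parent criterion, and its examples leave the narrow reading open.

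A reader might also infer that 3.39p is an isolated reversal, with every other such sign dating an event or a test. Section 3.39j shows otherwise.

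Finally, a sign can be altered when a PDF is converted to text. That cannot be ruled out. It is less likely here because ≥ appears correctly in 3.39b and 3.39c and because the two notes agree with each other.

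**Conclusion.** Read literally, both notes set a ceiling where a stability condition needs a floor, and nothing elsewhere corrects them. The point is a minor safety and eligibility correction.

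Its reach in 3.39p is limited to haemodynamically stable DVT or PE within 12 weeks of registration, unrelated to a catheter or procedure. In 3.39j it is limited to previously treated brain metastases. The number of such patients cannot be worked out from the documents.

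No alpha, power or sample-size figure changes. The planned maximum of 29 against 26 evaluable leaves 29 − 26 = 3 places for ineligibility and other losses, so an ineligible patient can be replaced.

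The conclusion rests on two assumptions: that the signs are printed this way in the source, and that 4 weeks and 28 days are the intended minimums. The second is an inference from the wording; the protocol does not state it.

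**What to change.** Check both signs against the source document. If they stand, make two changes in one amendment:
- 3.39p, first note: *for at least 4 weeks (≥ 4 weeks) prior to registration*.
- 3.39j, note: *for at least 28 days (≥ 28 days) prior to registration*.

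The drafting cost is small. The practical cost depends on current site practice. If sites already require 4 weeks of stability, nothing changes. If they apply the literal ceiling, some recently anticoagulated patients would wait up to 28 days.

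That wait is not trivial. Section 1.11 gives a typical second-line progression-free survival of 2 to 4 months. Assuming 30.4 days per month, 28 / (4 × 30.4) = 28 / 121.6 = 23%, and 28 / (2 × 30.4) = 28 / 60.8 = 46%.

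Registration must also fall within 30 days of pre-registration (Section 3.2). A full 28-day wait fits only if the dose is stable by day 30 − 28 = 2 after pre-registration. A dose that becomes stable on day 10 gives 10 + 28 = day 38, which is 8 days late. Sites can avoid this by delaying pre-registration: consent may precede it by up to 28 days (3.15), which allows 28 + 30 = 58 days from consent to registration.

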4.0 Test Schedule

	Active Monitoring Phase						
Tests and procedures	≤28 Days Prior to Pre- reg	≤14 days prior to reg	Baseline (Prior to Cycle 1 Day 1 treatment)	C1D15 ±3 days	C2 and Beyond (±5 days)	At PD, withdrawal, or removal	30 Days after last dose
History and exam, weight, ECOG PS		X		Х	Х	Х	Х
Height		Х					
Adverse event assessment				Х	Х	Х	Х
Informed Consent	Х						
ECHO/MUGA ^{R, 9}		Х			Х	Х	
Hematology: CBC/ differential		X	Х	Х	Х	Х	Х
Chemistry: AST, ALT, alk phos, T. bili, creatinine, calcium, glucose, Na, K		X	Х	Х	Х	X	Х
CPK and troponin ¹⁰			Х		Х		
Ophthalmic exam ^{R, 5, 6}		Х					
Imaging (CT/PET CT or MRI) and tumor measurement ¹		Х			X^4	X	
Urine pregnancy test ²		Х					
Central electronic/paper confirmation of a $BRAF^{V600E}$ mutation ⁷	Х						
Mandatory tissue sample (see Section 17.0) ^{R,8}			X				
Mandatory blood sample (see Section 14.0) ^R			Х		Х	Х	
Patient Medication Diary (Appendix I) ³				X	X	Х	

1 CT scans – chest, abdomen, and pelvis with IV and PO contrast; in the case of iodine contrast allergies an MRI of the abdomen and pelvis with gadolinium + a non-contrast chest CT is appropriate. Use same imaging throughout the study. Imaging at PD should only be repeated if not done within 28 days prior.

2 For women of childbearing potential only. Must be done \leq 7 days prior to registration.

3 The diary must begin the day the patient starts taking the medication and must be completed per protocol and returned at the end of every cycle to the treating institution.

4 To be completed prior to cycle 2 and prior to 3^{rd} cycle and subsequent odd cycles (± 5 days)

- 5 A full ophthalmic exam will be performed by an ophthalmologist at screening, and as needed during on-study treatment phase and include best corrected visual acuity, slit lamp examination, intraocular pressure, dilated fundoscopy and Ocular Coherence Tomography (OCT). Examination of the retina is required, especially to identify findings associated with serous retinopathy and RVO.
- 6 After baseline, patients receiving **binimetinib** should be assessed at every physical examination for decreased visual acuity using a gross perimetry test (as opposed to automated visual field testing). Symptomatic patients should be referred for a full ophthalmic consultation.
- 7 Results from a CLIA/CAP certified testing lab (commercial or institutional) that confirm the presence of a $BRAF^{V600E}$ mutation in the patient's tumor must be submitted for central review after the patient is pre-registered. See section 6.16 for detailed instructions.
- 8 Receipt of archival tumor tissue is not required for study registration and initiation of therapy. However, it is mandatory to receive the required tissue within 30 days from registration. See section 17.0.
- 9 ECHO/MUGA scans are to be performed at screening, on Cycle 2 Day 1, then every 12 weeks and at the end of treatment.
- 10 CPK and Troponin levels to be completed Cycle 1 Day 1 and Cycle 2 Day 1.
- R Research funded (see Section 19.0)

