Respiratory, thoracic and mediastinal	Pneumonitis, pulmonary fibrosis		
disorders	Grade 2	 Withhold binimetinib for up to 4 weeks. If improves to Grade 0-1, resume at a reduced dose. If not resolved within 4 weeks, permanently discontinue. 	
	Grade 3 or Grade 4	Permanently discontinue binimetinib.	
Investigations	Alanine aminotransferase or aspartate aminotransferase increased		

$\rightarrow \rightarrow$ Use the NCI C	Common Terminology Crit otherwise	eria for Adverse Events (CTCAE) version 5.0* unless e specified 🗲 🗲
CTCAE System/Organ/Class (SOC)	ADVERSE EVENT	ACTION**
	Grade 2	Maintain binimetinib dose.
		• If no improvement within 2 weeks, withhold binimetinib until improved to Grade 0-1 or to pretreatment/baseline levels and then resume at the same dose.
	Grade 3 or 4	See Other Adverse Reactions
	CPK increased	
Investigations	Grade 4 asymptomatic or Any Grade with symptoms or with renal impairment	 Withhold binimetinib dose for up to 4 weeks. If improved to Grade 0-1 resume at a reduced dose. If not resolved within 4 weeks, permanently discontinue binimetinib.
	Investigations-Other, specify	
	Recurrent Grade 2 or	Withhold for up to 4 weeks.
	First occurrence of any Grade 3	 If improves to Grade 0-1 or to pretreatment/baseline levels, resume at reduced dose. If no improvement, permanently discontinue encorafenib and binimetinib.
	First occurrence of any	Permanently discontinue or withhold for up to 4 weeks.
	Grade 4	 If improves to Grade 0-1 or to pretreatment/baseline levels, then resume at a reduced dose. If no improvement, permanently discontinue encorafenib and binimetinib.
	Recurrent Grade 3	Consider permanently discontinuing encorafenib and binimetinib.
	Recurrent Grade 4	Permanently discontinue.
Gastrointestinal	Nausea/Vomiting	
disorders	Grade 1-2	Maintain dose level of encorafenib and binimetinib. Promptly institute antiemetic measure.

\rightarrow \rightarrow Use the NCI Common Terminology Criteria for Adverse Events (CTCAE) version 5.0* unless otherwise specified \leftarrow		
CTCAE System/Organ/Class (SOC)	ADVERSE EVENT	ACTION**
	Grade 3	Interrupt dosing of encorafenib and binimetinib until resolved to Grade ≤ 1 . Then resume treatment as 1 reduced dose level of encorafenib. Resume treatment with binimetinib at the current dose if, in the judgement of the Investigator, the toxicity is considered to be unrelated to binimetinib, or at 1 reduced dose level.

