All patients who have initiated treatment will be considered evaluable for adverse event analyses. The rate of patients experiencing a grade 3+ adverse event will be reported. Further analyses of adverse event rates will be considered exploratory.

- 16.33 Correlative Research
 - 16.331 Additional mutations in BRAF or in other related genes as determined by next-generation sequencing from plasma samples will be used to investigate the mechanisms of resistance, either primary or acquired through real time monitoring of the BRAF mutational profile evolution.
 - 16.322 Changes in tumor biomarker

The absolute change and percentage change from baseline at each assessment of CA19-9 of CEA levels will be investigated.

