16.4 Safety Monitoring

16.41 Adverse Event Stopping Rule(s)

The stopping rules specified below are based on the knowledge available at study development. We note that the Adverse Event Stopping Rule may be adjusted in the event of either (1) the study re-opening to accrual or (2) at any time during the conduct of the trial and in consideration of newly acquired information regarding the adverse event profile of the treatment(s) under investigation. The study team may choose to suspend accrual because of unexpected adverse event profiles that have not crossed the specified rule below.

Accrual will be temporarily suspended to this study if at any time, we observe events considered to be at least possibly related to study treatment (i.e., an adverse event with attribute specified as "possible", "probable", or "definite") that satisfy the following:

If at any time, 3 of the initial 10 treated patients or 30% or more of all patients (when accrual is greater than 10 patients) have experienced a non-hematologic grade 4 or 5 adverse event.

We note that we will review Grade 4 and 5 adverse events deemed "unrelated" or "unlikely to be related", to monitor the emergence of a previously unrecognized treatment-related adverse event.

- 16.5 Data Monitoring and Reporting
 - 16.51 DSMB Reporting

The study chair(s) and the study statistician will review the study at least twice

per year to identify accrual, adverse event, and any endpoint problems that might be developing. The Mayo Clinic Cancer Center (MCCC) Data Safety Monitoring Board (DSMB) is responsible for reviewing accrual and safety data for this trial at least twice per year, based on reports provided by the MCCC Statistical Office.

Additionally, during the first Simon Stage, if and as soon as two patients have experienced a confirmed partial or complete response to therapy, then the study chair(s) and the study statistician will review the study to determine if the study can be opened for full accrual.

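### Scheduled CPK testing ends at Cycle 2 Day 1, so from Cycle 3 the binimetinib hold for asymptomatic Grade 4 CPK has no planned test behind it

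*Combined protocol and SAP*

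**What the plan says.** In section 4.0 the row "CPK and troponin" is marked at baseline and in the column headed "C2 and Beyond (±5 days"). It is blank at C1D15, at progression or withdrawal, and 30 days after the last dose. Footnote 10, attached to that row, states: "CPK and Troponin levels to be completed Cycle 1 Day 1 and Cycle 2 Day 1". The panel repeated through treatment is "Chemistry: AST, ALT, alk phos, T. bili, creatinine, calcium, glucose, Na, K", which does not contain CPK.

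Section 8.3 gives the CPK trigger for binimetinib as "Grade 4 asymptomatic or Any Grade with symptoms or with renal impairment". The action is to withhold for up to 4 weeks, resume at a reduced dose on recovery to Grade 0-1, and otherwise stop the drug permanently. Section 8.0 makes the dose-modification tables strict for the first two cycles; after that, "Thereafter, these modifications should be regarded as" guidelines. Section 13.1 allows up to 36 cycles of treatment.

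Two safety summaries depend on high-grade events being seen. Section 16.41 suspends accrual when 3 of the first 10 treated patients, or at least 30% of patients thereafter, "have experienced a non-hematologic grade 4 or 5 adverse event" that is at least possibly related to treatment. Section 16.325 adds: "The rate of patients experiencing a grade 3+ adverse event will be reported".

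**The concern.** A dose rule needs its input. The asymptomatic Grade 4 arm of the CPK row is by definition silent, so no complaint or examination finding leads the investigator to it. A site that follows footnote 10 has a pre-treatment CPK and one on-treatment CPK on day 29, and then none for as long as treatment continues.

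The protocol treats CPK as a real risk. Section 15.17 lists increased CPK among the very common effects of binimetinib (at least 10%, grade not stated). Section 15.187 calls rhabdomyolysis rare but serious.

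Patient safety is the main stake. A secondary one is that a Grade 4 rise nobody measures is absent from the 16.41 count and from the grade 3+ rate. A smaller matter is that a site reading only the grid could take CPK as continuing, while a site reading the footnote would stop.

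**Working it through.** The plan states no figure to reproduce. The check is a comparison of sections followed by a count of draws.

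**Is CPK scheduled anywhere from Cycle 3?**

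| Place | CPK from Cycle 3? |
|---|---|
| 4.0 grid row | Yes, if the column heading is read alone |
| 4.0 footnote 10 | No; last test is C2D1 |
| 4.0 chemistry panel, each cycle | No |
| 4.0 progression/withdrawal and 30-day visits | No; row is blank |
| 10.53 solicited events | No; myalgia is graded, CPK is not listed |

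**Which arms of the 8.3 trigger keep a prompt?**
- Symptomatic: yes. Myalgia is graded at each evaluation (10.53), and patients are told to report weakness or muscle pain (15.187).
- Renal impairment: yes. Creatinine is in the per-cycle panel.
- Asymptomatic Grade 4: none.

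**Draws omitted relative to Day 1 of every cycle.** Cycles are 28 days (7.1), so Day 1 of cycle n falls on day 28(n − 1) + 1. C2D1 is day 29, C3D1 is day 57, and the next are days 85, 113 and 141. Nominal days are used, ignoring the ±5-day window.

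| Time on treatment | Source | Days | Draws after C2D1 |
|---|---|---|---|
| 7 weeks | 1.15, minimum | 49 | 0 |
| 2 months | 1.11, second-line PFS (assumption) | 60.9 | 1 (day 57) |
| 4 months | 1.11, second-line PFS (assumption) | 121.8 | 3 (days 57, 85, 113) |
| 21 weeks | 1.15, median | 147 | 4 (days 57, 85, 113, 141) |
| 110 weeks | 1.15, maximum | 770 | 26 (C3 day 57 to C28 day 757) |
| 36 cycles | 13.1, ceiling | 1,008 | 36 − 2 = 34 |

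The 1.15 figures come from a series of 17 patients on various BRAF-directed regimens, only 6 of whom received a BRAF plus MEK combination. The 1.11 figures are for second-line chemotherapy. Neither is a forecast for this trial.

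**A 12-week interval after C2D1.** Draws fall on days 29 + 84k, that is 113, 197 and so on. One falls by day 147. By day 1,008, k ≤ (1,008 − 29)/84 = 11.65, so 11 draws, the last on day 29 + 84 × 11 = 953.

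**Weight of one missed event under 16.41.** It is one of the 3 needed in the first 10 patients. At 26 patients, 0.30 × 26 = 7.8, so 8 are needed and it is one of those 8.

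**The case against.** The strongest reply is that there is no internal conflict. The grid has no separate C2D1 column, so a test wanted only on that day has to be marked in the shared column and narrowed by a footnote, as footnote 4 does for imaging and footnote 9 for ECHO/MUGA. On that reading the schedule is a deliberate choice, and both CPK tests fall in the two cycles during which the dose rules are strict. This may well be what was intended. It does not close the gap, though: footnotes 4 and 9 narrow the column but continue testing, and footnote 10 stops without giving a reason. A guideline also needs a value before anyone can apply it.

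Second, the exposed group is small. Symptoms and creatinine still prompt the other two arms, unscheduled CPK is allowed, 3.39m excludes neuromuscular disorders associated with raised CK, and 15.189a discourages new strenuous exercise. All of this stands, and it confines the point to one arm of one row.

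Third, harm cannot be quantified. That also stands: the draw counts measure the omitted testing, not missed events. The effect on 16.41 needs a rise judged at least possibly related, in a patient with no other qualifying event; the effect on the grade 3+ rate needs it to be that patient's only such event.

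Fourth, more testing could bring more symptomless laboratory events into the suspension rule, and the CPK row carries no research-funding mark, so who would pay is unclear. The first is a real consequence, but the rule as written is meant to count those events. The second is a small cost for one analyte.

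**Conclusion.** The point holds. As written, the schedule leaves the asymptomatic Grade 4 CPK hold without a planned input from Cycle 3 to the end of treatment. Against per-cycle testing, the shortfall is 1 to 3 draws if treatment lasts 2 to 4 months, 4 at 21 weeks, and at most 34; a patient treated only 7 weeks loses none. This rests on footnote 10 governing over the column heading and on nominal 28-day cycles. How many holds or countable events would be missed cannot be estimated from the documents.

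This is an inexpensive improvement in safety monitoring that should be made. It is not a flaw in the main analysis: the primary endpoint, sample size and error rates are untouched.

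**What to change.** Amend footnote 10 so that CPK is drawn at C1D1 and then with the chemistry panel on Day 1 of each cycle from Cycle 2 onward, leaving troponin as it is. The footnote and the grid would then agree for CPK. Alternatively, state a longer continuing interval, following the pattern of footnote 9 (every 12 weeks and at end of treatment).

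The cost is one footnote amendment and one added analyte on blood already drawn. Per-cycle testing adds 4 results for a patient treated 21 weeks and at most 34 over 36 cycles. The 12-week interval adds 1 and at most 11 on-treatment results, plus an end-of-treatment test if that is adopted. The downside is possibly more binimetinib holds, some for rises that cause no symptoms, and more laboratory events entering the 16.41 count.
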